5.2. Exclusion Criteria

A patient will be excluded from this study if she/he meets any of the following criteria.

1. Patients with confirmed stage 1 through stage 3c breast cancer currently receiving chemotherapy, radiation therapy, immunotherapy, or biotherapy for breast cancer.
2. Patients with mBC that have received prior capecitabine or HER2 directed TKI therapy.
3. Currently using drugs that have been implicated as causing microscopic colitis/watery diarrhea, such as acarbose, aspirin, proton pump inhibitors, nonsteroidal anti-inflammatory drugs (NSAIDs), histamine H₂-receptor antagonists, selective serotonin reuptake inhibitors, and ticlopidine ([Pardi, 2017](#)).
4. Major surgery within <28 days of starting treatment or received chemotherapy, investigational agents, or other cancer therapy, except hormonal therapy (eg, tamoxifen, aromatase inhibitors), <14 days prior to the initiation of investigational products.
5. Active uncontrolled cardiac disease, including cardiomyopathy, congestive heart failure (New York Heart Association functional classification of ≥ 2 ; including individuals who currently use digitalis, beta-blockers, or calcium channel blockers specifically for congestive heart failure), unstable angina, myocardial infarction within 12 months of enrollment, or ventricular arrhythmia.
6. QTc interval >0.450 seconds (males) or >0.470 (females), or known history of QTc prolongation or Torsade de Pointes (TdP).
7. Diagnosis of inflammatory bowel disease.
8. Screening laboratory assessments outside the following limits:

Laboratory Parameters	Required Limit for Exclusion
Absolute neutrophil count (ANC)	$\leq 1,000/\mu\text{l}$ ($\leq 1.0 \times 10^9/\text{L}$)
Platelet count	$\leq 50,000/\mu\text{l}$ ($\leq 100 \times 10^9/\text{L}$)
Hemoglobin	$\leq 8 \text{ g/dL}$ (transfusions allowed) Transfusions must be at least 14 days prior to initiation of treatment
Total bilirubin	$>1.5 \times$ institutional upper limit of normal (ULN) (in case of known Gilbert's syndrome, $<2 \times$ ULN is allowed)
Aspartate aminotransferase (AST) and/or alanine aminotransferase (ALT)	$>2.5 \times$ institutional ULN ($>5 \times$ ULN if liver metastases are present in mBC patients)
Creatinine	Creatinine clearance $<30 \text{ mL/min}$ (as calculated by Cockcroft-Gault formula ^a or Modification of Diet in Renal Disease [MDRD] formula ^b)
International Normalized Ratio (INR)	≥ 1.5

^a [Cockcroft and Gault, 1976](#)

^b [Levey et al, 1999](#)

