6.1.1. Neratinib Dose Adjustment

Neratinib dose adjustment and/or discontinuation and/or management of toxicity should be performed according to [Appendix 2](#) and [Section 10.1](#).

Recommended dose reductions for the -1 and -2 dose levels of neratinib are listed in [Table 3](#).

Table 3: Dose Reduction Levels for Neratinib-Related Toxicity

Dose Level	Neratinib
Recommended Starting Dose	240 mg
First dose reduction	200 mg
Second dose reduction	160 mg
Third dose reduction	120 mg

mg = milligrams

If doses of neratinib are held, study procedures for that cycle will proceed on schedule as planned, without any delay. Missed dose(s) of neratinib (i.e., any dose that is not administered within the protocol-defined administration window) will not be made up. **Note: Patients should take one dose per calendar day.** The dose adjustment guidelines represent the minimum set of measures the Investigator must follow. However, additional measures may be taken, as necessary, for certain patients per the Investigator's medical judgment. All dose modifications/adjustments should be documented in the patient's source file.

Once the neratinib dose has been reduced for a patient, all subsequent cycles must be administered at that dose, unless further dose reduction is required. Dose re-escalation will only be permitted if explicitly approved in advance by the Sponsor. Evidence of this approval must be contained within the patient's source file.

Patients must discontinue the investigational product if a criterion for withdrawal is met (see [Section 10.1](#)).

Reintroduction of the discontinued investigational product at a later time during the active treatment phase is not permitted.

Detailed rules for dose adjustments of neratinib in case of toxicity, including the dose levels to which the investigational product should be adjusted, are provided in [Appendix 2](#).

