10. PATIENT WITHDRAWAL AND REPLACEMENT

10.1. Investigational Product Discontinuation

Patients **must** be discontinued from **investigational product** under the following circumstances listed below and in [Appendix 2](#), unless otherwise agreed with the Medical Monitor:

- If the patient requires more than 2 dose reductions of neratinib (see [Appendix 2](#))
- If neratinib is withheld due to an SAEs for >28 days. Patients who are clinically benefiting from therapy with neratinib may be resumed on therapy after 28 days if approved in advance by the Sponsor
- Disease recurrence
- Initiation of alternative anti-cancer therapy. Any concurrent chemotherapy, radiotherapy (including palliative radiotherapy), surgery related to cancer, anticancer immunotherapy, or other anticancer treatments including other investigational agents (see [Section 7.3](#)).
- Pregnancy (see [Section 13.4](#))
- Investigator request
- Patient request (i.e., withdrawal of consent for treatment)
- AEs/toxicity

Withdrawal due to AE should be distinguished from withdrawal due to other causes, and recorded on the appropriate AE page of CRF. If a patient withdraws due to toxicity, even if discontinuation is not otherwise required per protocol guidelines, the withdrawal should be classified as withdrawal due to AE.

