APPENDIX 2. INVESTIGATIONAL PRODUCT DOSE ADJUSTMENT FOR TOXICITY

1. Dose adjustment levels

Recommended dose reductions for the -1 and -2 dose levels of **neratinib** and **capecitabine** are listed in [Table 3](#) in [Section 6.1.1](#) and in [Table 6](#) in [Section 6.3.1](#).

2. Toxicities Requiring Investigational Product Dose Adjustments

General Toxicities:

The guidelines for dose adjustments of **neratinib** and **capecitabine** for general toxicities due to the combination of **neratinib** plus **capecitabine** are shown in [Table A2.1](#).

Table A2.1. General Toxicities Requiring Dose Adjustment of Neratinib

NCI CTCAE v.4.0	Action
Grade 2 adverse reaction	
• 1st appearance	• Hold neratinib and capecitabine until event resolves to Grade ≤ 1 ; then resume neratinib at the starting dose level.
• 2nd appearance	• Hold neratinib and capecitabine until event resolves to Grade ≤ 1 ; then resume neratinib at 160 mg and capecitabine at 1100 mg/m ² (550 mg/m ² BID).
• 3rd appearance	• Hold neratinib and capecitabine until event resolves to Grade ≤ 1 ; then resume neratinib at 120 mg and capecitabine at 750 mg/m ² (375 mg/m ² BID).
• 4th appearance	• Discontinue neratinib and capecitabine permanently.
Grade 3 adverse reaction	
• 1st appearance	• Hold neratinib and capecitabine until event resolves to Grade ≤ 1 ; then resume neratinib at 160 mg and capecitabine at 1100 mg/m ² (550 mg/m ² BID).
• 2nd appearance	• Hold neratinib and capecitabine until event resolves to Grade ≤ 1 ; then resume neratinib at 120 mg and capecitabine at 750 mg/m ² (375 mg/m ² BID).
• 3rd appearance	• Discontinue neratinib and capecitabine permanently.
Grade 4 adverse reaction	
• 1st appearance	• Discontinue neratinib and capecitabine permanently OR if Investigator deems it to be in the patient's best interest to continue, hold neratinib and capecitabine until resolved to Grade ≤ 1 ; then resume neratinib at 120 mg and capecitabine at 750 mg/m ² (375 mg/m ² BID). • If the event occurs again despite one dose reduction, permanently discontinued neratinib .

Abbreviations: BID: twice daily; NCI CTCAE v4.0, National Cancer Institute Common Terminology for Adverse Events Version 4.0.

Gastrointestinal Toxicity:

Guidelines for adjusting doses of **neratinib** and **capecitabine** in the event of gastrointestinal toxicity diarrhea are shown in [Table A2.2](#).

Table A2.2. Gastrointestinal Toxicities Requiring Dose Adjustment of Neratinib and Capecitabine

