Patients who experience \geq Grade 3 diarrhea requiring IV fluid treatment or any signs or symptoms of hepatotoxicity such as worsening of fatigue, nausea, vomiting, right upper quadrant pain or tenderness, fever, rash or eosinophilia should be evaluated for changes in liver function tests. Fractionated bilirubin and prothrombin time must also be collected during hepatotoxicity evaluation.

Table A2.4. Liver Function Test Abnormalities Requiring Dose Adjustment of Neratinib

NCI CTCAE V4.0	Action
Grade 3 ALT (>5 – 20x ULN) OR Grade 3 bilirubin (>3-10x ULN)	
 Hold neratinib and capecitabine until recovery to \leq Grade 1 for patients with ALT \leq Grade 1 at baseline OR \leq Grade 2 for patients with Grade 2 ALT at baseline. Evaluate alternative causes. For patients with ALT $<$ Grade 1 at baseline: Resume neratinib at the next lower dose level (160 mg) and capecitabine at the next lower dose level (1100 mg/m² [550 mg/m² BID])^a if recovery to \leq Grade 1 occurs within 4 weeks. If Grade 3 ALT or bilirubin occurs again despite one dose reduction, permanently discontinue neratinib and capecitabine.
Grade 4 ALT (>20x ULN) OR Grade 4 Bilirubin (>10x ULN)	
 Permanently discontinue neratinib and capecitabine. Evaluate alternative causes.

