ALT >3x ULN AND Total bilirubin >2x ULN AND Alkaline phosphatase <2x ULN (potential Hy's law indicators of drug-induced liver damage)	
 Hold neratinib and capecitabine. The patient should return to the investigational site and be evaluated as soon as possible, preferably within 48 hours from awareness of the abnormal results. This evaluation should include laboratory tests, detailed history and physical assessment and for oncology studies, the possibility of hepatic neoplasm (primary or secondary) should be considered. In addition to repeating AST and ALT, laboratory tests should include albumin, total bilirubin, direct bilirubin, PT and alkaline phosphatase. A detailed history, including relevant information, such as review of ethanol, concomitant medications, recreational drug and supplement consumption, family history, sexual history, travel history, history of contact with a jaundiced patient, surgery, blood transfusion, history of liver or allergic disease, and work exposure, should be collected. Further testing for acute hepatitis A, B, or C infection and liver imaging (eg, biliary tract) may be warranted. All cases confirmed on repeat testing as meeting the criteria mentioned above (i.e., ALT $>$ 3 x ULN associated with bilirubin $>$ 2 x ULN and alkaline phosphatase $<$ 2 x ULN), with no other cause for liver function test abnormalities identified at the time should be considered potential Hy's Law cases, irrespective of availability of all the results of the investigations performed to determine etiology of the abnormal liver function tests. Contact the Sponsor immediately to discuss next steps, including evaluation of alternative causes, and management of investigational product. These events must be reported as SAEs.

Abbreviations; ALT=alanine aminotransferase; AST: aspartate aminotransferase; BID: twice daily; PT: prothrombin time; SAE: serious adverse event; ULN: upper limit of normal.

NOTE: During evaluation of hepatotoxicity, bilirubin must be fractionated, prothrombin time must be measured, and liver imaging should be considered.

^a Since capecitabine is provided as 150 mg or 500 mg tablets, it is recommended that the capecitabine dose reduction(s) is rounded down to the nearest 500 mg or multiple of 150 mg for the BID dose. If the patient's body surface area is >2.0, the standard of care for the study center can be utilized for capecitabine mg/m² dosing.

Left Ventricular Ejection Fraction Toxicity

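### In Table A2.4 the recovery target after a Grade 3 bilirubin event follows baseline ALT, so with Grade 2 baseline ALT the row's hold can end at bilirubin up to 3 × ULN

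*Protocol*

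**What the plan says.** **Table A2.4, Grade 3 row (Protocol, Appendix 2).** The trigger is ALT above 5 and up to 20 × ULN, "OR Grade 3 bilirubin (>3-10x ULN"). Both drugs are then held. The hold ends at Grade 1 or lower if baseline ALT was Grade 1 or lower, and at or below "Grade 2 for patients with Grade 2 ALT at baseline". Baseline bilirubin is not mentioned, and bilirubin has no target of its own. The row's restart instruction (next lower dose level, recovery to Grade 1 or lower within 4 weeks) appears only under a heading for patients with lower baseline ALT.

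**Table A2.4, potential Hy's Law row.** A separate hold applies when "ALT >3x ULN AND Total bilirubin >2x ULN AND Alkaline phosphatase <2x ULN". No laboratory value is printed for ending it. The site must contact the sponsor at once about next steps and drug management, and must report the event as an SAE.

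**Table A2.1, Grade 3 adverse reaction.** The instruction begins "Hold neratinib and capecitabine until event resolves to Grade" and sets the target at Grade 1 or lower.

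**Section 5.2, exclusion criterion 8.** Total bilirubin above 1.5 × ULN excludes a patient; below 2 × ULN is allowed in known Gilbert's syndrome. ALT above 2.5 × ULN excludes, relaxed to above 5 × "ULN if liver metastases are present in mBC patients". The table has no alkaline phosphatase (ALP) limit.

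**Section 6.1.1.** "The dose adjustment guidelines represent the minimum set of measures the Investigator must follow".

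**The concern.** Letting ALT return to a raised baseline is sensible, because a patient who entered with Grade 2 ALT may never reach Grade 1. The same reasoning does not carry over to bilirubin, which is capped at entry whatever the ALT. Where Tables A2.2 and A2.3 relax a recovery target, they relax it to the baseline of the same event. In this row the baseline of one analyte relaxes the target for another.

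What is at stake is the safety of a few patients with liver metastases. After a Grade 3 bilirubin event, the liver table's own minimum requirement can be met while bilirubin is still well above what the protocol accepts at entry. An investigator may hold longer, but this row does not require it.

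**Working it through.** No sample size, power or error rate bears on this point. The check is arithmetic on the printed cut-offs and a comparison of the rules.

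**1. Bilirubin ceiling at release.** The row starts Grade 3 bilirubin above 3 × ULN, so Grade 2 reaches up to 3 × ULN. For Grade 2 baseline ALT, the row's hold therefore ends at bilirubin ≤ 3 × ULN.

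**2. Comparison with entry (Section 5.2).**
- Usual limit: 3 / 1.5 = 2.0 times.
- Gilbert's allowance: 3 / 2 = 1.5 times.

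**3. Who is affected.** The documents do not print the lower bound of Grade 2 ALT. Assume it lies at 2.5 or at 3 × ULN. Either way, a patient without liver metastases is excluded above 2.5 × ULN and cannot have Grade 2 ALT at screening. That leaves metastatic patients with liver metastases, who may enter with ALT up to 5 × ULN. The SAP (Section 3) takes baseline as the last value on or before the first dose, so a rise after screening could add another patient, but this would be an exception.

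**4. What the Hy's Law row covers.** Every event here begins with bilirubin above 3 × ULN, so the bilirubin criterion (above 2 × ULN) is met at onset. Two conditions remain:

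| During the event, while bilirubin is > 2 × ULN | Hy's Law hold? |
|---|---|
| ALT > 3 × ULN and ALP < 2 × ULN at some point | Yes; no printed release, sponsor involved |
| ALP ≥ 2 × ULN throughout | No |
| ALT ≤ 3 × ULN throughout | No |

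Because the hold has no laboratory release, a patient who met the criteria at onset is not freed when ALT later falls to 3 × ULN or below. The gap is therefore limited to patients who never met the criteria, mainly those with ALP ≥ 2 × ULN or with ALT already ≤ 3 × ULN. The first profile is possible from enrolment because there is no ALP entry limit.

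**5. Which table governs.** For one and the same Grade 3 bilirubin event, Table A2.1 gives Grade 1 or lower, while Table A2.4 gives Grade 2 or lower if baseline ALT was Grade 2. Nothing in Appendix 2 or Section 6.1.1 says which prevails.

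**6. After the change.** The release ceiling becomes the top of Grade 1 bilirubin. The documents do not print it; over an assumed range of 1.5 to 2 × ULN, it is 1.0 to 1.33 times the usual entry limit (1.5/1.5 and 2/1.5).

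**The case against.** The strongest reply has four parts.

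- **Hy's Law.** A reader might infer that this protection lapses once ALT drops to 3 × ULN, and so count most combinations of ALT and ALP at recovery as unprotected. The documents do not support that. The row acts when its criteria are met and prints no release, so history matters. This part of the reply stands and narrows the gap.
- **Table A2.1.** A reader might infer that nothing else in the protocol keeps the drugs on hold. That is also too strong. A laboratory result that changes dosing is an adverse event (Section 13.1.2), and Table A2.1 holds both drugs to Grade 1 or lower after Grade 2 and Grade 3 adverse reactions. It may well apply. But it is headed as general toxicities and A2.4 is the liver-specific table, so a site could reasonably follow A2.4. The conflict itself needs resolving.
- **No printed restart.** A reader might infer that the protocol directs sites to restart both drugs at bilirubin up to 3 × ULN. It does not: the row ends the hold for this group but prints no resume instruction for it. The defect lies in the hold target, with a missing restart rule beside it.
- **Intent.** The Grade 2 target was probably meant for ALT events only. That is the natural clinical purpose, but the row does not say so.

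Section 6.1.1 permits a longer hold on medical judgment. It also makes these rules the minimum, and the minimum is what is set too loosely here.

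**Conclusion.** The point holds in limited form. As printed, the Grade 3 row lets a raised baseline ALT loosen the recovery target for bilirubin, to a ceiling of 2.0 times the usual entry limit (1.5 times in Gilbert's syndrome). It bites only for a patient with Grade 2 baseline ALT, an on-study Grade 3 bilirubin event, and a course that never met the potential Hy's Law criteria, and only if Table A2.1 is read as not applying.

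It is minor. The study plans 3-5 patients, the subgroup is narrow, and the primary endpoint is unaffected. The conclusion rests on the literal wording of the row and on Grade 2 ALT starting at 2.5 or 3 × ULN, which the documents do not print.

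**What to change.** Replace the single target in the Grade 3 row of Table A2.4 with one per analyte:

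- *ALT: Grade 1 or lower, or Grade 2 or lower if ALT was Grade 2 at baseline.*
- *Bilirubin: Grade 1 or lower (below 2 × ULN in known Gilbert's syndrome), whatever the baseline ALT.*
- *Both must be met before restart.*

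Then apply the row's existing restart step (next lower dose level) and its 4-week limit to the Grade 2 baseline ALT group as well. Word it as a step down, not a fixed 160 mg, or a patient already taking 160 mg would restart with no reduction. Refer longer holds to Section 10.1, where patients who are benefiting after an SAE hold "may be resumed on therapy after 28 days if approved in advance by the Sponsor", and to the note after Table A2.5, under which adverse-event holds beyond 28 days should lead to withdrawal from active treatment. The Hy's Law row can stay as it is.

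The cost is an edit to one table cell. No new tests are needed, because the liver panel for metastatic patients already includes total bilirubin, ALT and ALP (Table A1.2, footnote k). The downside is a slightly longer hold for a few patients.

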NOTE; patients with mBC cannot be exposed to capecitabine until after completion of the second study colonoscopy procedure.

In extended adjuvant patients with stage 1 to 3c breast cancer, patients will return to the clinic approximately every 3 months for safety assessments. End of Treatment (EOT) visit is planned on upon completion of 1 year of treatment, followed by Safety Follow-up Visit 28 days after the last dose of neratinib.

In patients with mBC, clinic visits during the active treatment phase are planned on Day 1 of Cycle 1, Cycle 2, and each subsequent cycle. Treatment discontinuation visit is planned 0-3 days after the last dose, followed by a Safety Follow-up Visit 28 days after the last dose of neratinib.

Assessments required throughout the study are summarized in the Schedule of Study Procedures ([Appendix 1](#)).

Patients may be discontinued from investigational product or from the study, as described in [Section 10](#) and [Section 11](#).

The primary endpoint of the study is change from baseline in pathological findings in colon biopsies after the first 28 days of neratinib. The secondary endpoint is the incidence and severity of diarrhea during the first 28-day cycle.

The study will end when all patients have been followed-up for 28 days after the last dose of neratinib.

Approximately 3-5 patients will be enrolled at approximately 2 centers.

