NCI CTCAE V4.0	Action

 Grade 1 Diarrhea [Increase of <4 stools per day over baseline; mild increase in ostomy output compared to baseline.] OR Grade 2 Diarrhea [Increase of 4-6 stools per day over baseline; moderate increase in ostomy output compared to baseline;] lasting <5 days OR Grade 3 Diarrhea [Increase of ≥ 7 stools per day over baseline; incontinence; hospitalization indicated; severe increase in ostomy output compared to baseline limiting self-care activities of daily living (ADL)] lasting ≤ 2 days 
 Persisting and intolerable Grade 2 Diarrhea lasting ≥ 5 days despite being treated with optimal medical therapy, or associated with fever, dehydration, or Grade 3-4 neutropenia OR Grade 3 Diarrhea lasting > 2 days despite being treated with optimal medical therapy, or associated with fever, dehydration, or Grade 3-4 neutropenia OR Any Grade 4 diarrhea [Life-threatening consequences; urgent intervention indicated] 	
 Adjust anti-diarrheal treatment, as per the guidelines for management of diarrhea at the first onset of diarrhea (refer to Section 6.2 and Section 7.2). Continue neratinib and capecitabine at full dose. Instruct patient to follow dietetic recommendations in the guidelines for management of diarrhea (refer to Section 7.2). Fluid intake of ~ 2L should be maintained to avoid dehydration. Once the event resolved to \leq Grade 1 or baseline, start loperamide 4 mg with each subsequent neratinib administration. 
 Adjust anti-diarrheal treatment, as per the guidelines for management of diarrhea at the first onset of diarrhea (refer to Section 6.2 and Section 7.2). Hold neratinib and capecitabine until recovery to \leq Grade 1 or baseline. Instruct patient to follow dietetic recommendations of the guidelines for management of diarrhea. Fluid intake of ~ 2L should be maintained, intravenously if needed. If recovery occurs: 
 ≤ 1 week after withholding treatment, resume same dose of neratinib and capecitabine. Within 1-4 weeks after withholding treatment, reduce neratinib dose to the next lower dose level and maintain the same dose of capecitabine. If event occurs a 2nd time and the neratinib dose has not already been decreased, reduce neratinib dose to the next lower dose level and maintain the same dose of capecitabine. If neratinib dose has already been reduced, then reduce the dose of capecitabine to 1100 mg/m^2^a (550 mg/m^2 BID) (maintain same dose of neratinib) If subsequent events occur, reduce the dose of neratinib or capecitabine to the next lower dose level in an alternate fashion (i.e., reduce capecitabine to 750 mg/m^2 (375 mg/m^2 BID) if neratinib was previously reduced, or reduce neratinib to 120 mg if capecitabine was previously reduced.. Once the event resolved to \leq Grade 1 or baseline, start loperamide 4 mg with each subsequent neratinib administration.

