2.3.2 Neratinib Adjustments

Neratinib may be dose-adjusted/reduced due to neratinib-related toxicity. The prescribed dose levels can be 240mg, 200mg, 160mg, 120mg, with the latter three doses representing the reduction levels. If doses of neratinib are held, study procedures for that cycle will proceed on schedule as planned, without any delay. Missed dose(s) of neratinib (i.e., any dose that is not administered within the protocol-defined administration window) will not be made up. **Note: Patients should take one dose per calendar day.** The dose adjustment guidelines represent the minimum set of measures the Investigator must follow. However, additional measures may be taken, as necessary, for certain patients per the Investigator's medical judgment. All dose modifications/adjustments should be documented in the patient's source file.

Once the neratinib dose has been reduced for a patient, all subsequent cycles must be administered at that dose, unless further dose reduction is required. Dose re-escalation will only be permitted if explicitly approved in advance by the Sponsor. Evidence of this approval must be contained within the patient's source file.

Patients must discontinue the investigational product if a criterion for withdrawal is met. Reintroduction of the discontinued investigational product at a later time during the active treatment phase is not permitted.

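### Protocol Table 3 makes 200 mg the first neratinib reduction but Table A2.4 labels 160 mg the next level down, so the unspecified first step in the diarrhea table (A2.2) can be read as either dose

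*Protocol*

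**What the plan says.** Protocol Section 6.1.1, Table 3, starts neratinib at 240 mg and labels 200 mg the first reduction, 160 mg the second and 120 mg the third. The sentence introducing this three-step table mentions only two levels: "Recommended dose reductions for the -1 and -2 dose levels of neratinib are listed in" Table 3. Appendix 2, item 1, uses the same two-level wording and points back to Table 3. SAP 2.3.2 gives the same set of doses: "The prescribed dose levels can be 240mg, 200mg, 160mg, 120mg, with the latter three doses representing the reduction levels".

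The toxicity tables in Appendix 2 read differently. For Grade 3 ALT or bilirubin, Table A2.4 says "Resume neratinib at the next lower dose level (160 mg") and, in the same sentence, takes capecitabine to 1100 mg/m², which is level -1 in Table 6. Tables A2.1 (Grades 2 and 3), A2.3 and A2.8 also use 160 mg as the first reduced dose.

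Table A2.2, on diarrhea, gives no milligram figure for its first neratinib step: "Within 1-4 weeks after withholding treatment, reduce neratinib dose to the next lower dose level". Its only printed neratinib dose comes later: "reduce neratinib to 120 mg if capecitabine was previously reduced".

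Section 6.1.1 says that Appendix 2 holds the detailed adjustment rules, "including the dose levels to which the investigational product should be adjusted".

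**The concern.** From 240 mg, 160 mg is the second reduction in Table 3 but the next level down in Table A2.4. Where a table prints the dose, a site can follow the printed figure despite the conflicting label. Table A2.2 does not allow that for its first step, so the reader must take the dose from elsewhere, and the protocol offers two answers.

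What is at stake is clear and consistent dosing. Diarrhea is the toxicity that the trial studies. The first A2.2 reduction can occur within Cycle 1, before the second colonoscopy, and in either disease group. Two sites that both follow the protocol could reduce similar patients to different doses.

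**Working it through.** No powered calculation is involved. The check compares the passages and traces Table A2.2 under each set of levels.

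**Inputs**

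| Source | Neratinib levels below 240 mg |
|---|---|
| Table 3 | 200 (first), 160 (second), 120 (third) |
| SAP 2.3.2 | 200, 160, 120; order not labelled |
| Table A2.1, Grade 2 (2nd and 3rd appearance) and Grade 3 (1st and 2nd) | 160, then 120 |
| Table A2.3, Grade 2 | 160 |
| Table A2.4, Grade 3 | 160, labelled the next level down |
| Table A2.8 | 160 |
| Table A2.2, first step | no figure |
| Table A2.2, later step | 120 |

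Call 240/200/160/120 ladder A (Table 3) and 240/160/120 ladder B (Appendix 2 usage).

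**First A2.2 step from 240 mg**
- Ladder A: 200 mg, or 200/40 = 5 tablets. Reduction (240 − 200)/240 = 16.7%.
- Ladder B: 160 mg, or 160/40 = 4 tablets. Reduction (240 − 160)/240 = 33.3%.
- Difference: 40 mg a day, one tablet. Ladder B is (200 − 160)/200 = 20% below ladder A.
- The planned Cycle 1 dose is 28 × 240 = 6,720 mg. Each 7 days at the reduced dose separates the readings by 7 × 40 = 280 mg, and 280/6,720 = 4.2%.

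**Later A2.2 step, after neratinib and then capecitabine have been reduced**
- Ladder B moves from 160 to 120 mg, which matches the printed 120 mg.
- Ladder A moves from 200 to 160 mg, so the printed 120 mg skips a level.
- This step presupposes a capecitabine reduction. It therefore reaches only metastatic patients after the second colonoscopy, because "patients with mBC cannot be exposed to capecitabine until after completion of the second study colonoscopy procedure".

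**Do the cross-references settle it?** Appendix 2, item 1, sends the reader to Table 3, which gives 200 mg. Section 6.1.1 sends the reader to Appendix 2 for the levels. The pointers are circular and no order of precedence is stated.

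**Could Table A2.4 mean a patient already at 200 mg?** It states no such condition. It also pairs the step with capecitabine level -1, the first reduction from the starting dose, which favours reading 160 mg as a first step too.

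**The case against.** The two readings of Table A2.2 are not equally direct. Item 1 of Appendix 2 states where the levels are listed, and following it gives 200 mg. Reaching 160 mg means borrowing the label from the liver table or inferring it from the later 120 mg step. This stands, but it does not remove the ambiguity, because that 120 mg step is in Table A2.2 itself and does not fit Table 3 taken stepwise.

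One could also argue that 160 and 120 mg are combination-therapy steps and Table 3 is the monotherapy ladder, since Tables A2.1 and A2.4 also adjust capecitabine. The protocol does not say so, and Table A2.3, which adjusts neratinib alone, also goes to 160 mg.

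The practical weight is modest. There are 3-5 patients and the difference is one tablet. A hold of at least 7 days before the reduction would remove 7 × 240 = 1,680 mg, or 25% of the planned Cycle 1 dose, far more than the 4.2% a week at issue. The step may not arise at all. If the Study 6201 rate of dose reduction for diarrhea under loperamide prophylaxis applied (11/137 = 8.0%, over about a year), the chance of at least one such patient would be 1 − 0.92³ = 22% to 1 − 0.92⁵ = 34%. At the Study 3004 rate without prophylaxis (26.4%) it would be 60% to 78%. Both rates are assumptions for this regimen and population, and Cycle 1 alone would be lower.

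Safeguards exist. Section 7.2 sends investigators to the Sponsor or Medical Monitor when diarrhea management is in doubt, and Section 6.1.1 says "The dose adjustment guidelines represent the minimum set of measures the Investigator must follow". These reduce the risk, but neither states the level. A reader might infer that a site using a single table would find nothing to query. That is not so for Table A2.2, which forces the site to look elsewhere. The difficulty is that it can find either of two answers.

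**Conclusion.** The point holds as an internal inconsistency in the dosing text, wrong as written and worth fixing. Table 3 and Table A2.4 disagree on the first level below 240 mg, and Table A2.2 leaves its first step open to 200 mg or 160 mg. In Tables A2.1, A2.3, A2.4 and A2.8 the printed dose governs and only the level label conflicts. The size rests on the 240 mg starting dose and 40-mg tablets.

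Three stronger readings are not supported:
- A reader might infer that the SAP also makes 200 mg the first reduction. It lists 200 mg among the reduction levels without saying which comes first.
- A reader might infer that Section 10.1, which stops neratinib after more than two reductions, contradicts Table 3's third reduction. The Medical Monitor can agree otherwise, and the documents do not say whether the limit counts dose changes or levels. That is a separate matter.
- A reader might infer harm to the trial's conclusions. There is no powered comparison, enrollment is set by feasibility, and SAP 6.7.1 presents neratinib exposure as a listing.

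**What to change.** The sponsor's medical team should reconcile Protocol Section 6.1.1 with Table 3, Appendix 2 item 1, Tables A2.1 to A2.4 and A2.8, and SAP 2.3.2 to one set of neratinib dose levels. The two lead-ins that mention only levels -1 and -2 should then match that set, and Table A2.2 should print the milligram figure wherever it calls for the next level down. While doing this, the team should check that the agreed levels are consistent with the Section 10.1 limit on reductions. No view is given here on which dose or limit is right.

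The cost is a protocol clarification and, if the levels change, a matching edit to SAP 2.3.2. SAP 6.7.1 needs no separate change, because the SAP already states its levels in milligrams. No extra patients or data are needed.
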